9.9 Health Economics OR Medical Resource Utilization and Health Economics

Health Economics/Medical Resource Utilization and Health Economics parameters will not be evaluated in this study.

10 STATISTICAL CONSIDERATIONS

10.1 Sample Size Determination

The sample size calculation is driven by the power to compare mean percentage change from baseline in EASI score at Week 16 between BMS-986166 or branebrutinib versus placebo. Thirty participants per group will provide 84% power to detect a treatment difference (versus placebo) of 30 % at the type I error of $\alpha = 0.05$ (1-sided), assuming a common standard deviation of 43%. The assumed treatment difference of 30% is similar to the mean difference observed from historical data on approved drugs across different mechanism of actions. No adjustment will be made for multiplicity.

Assuming a 15% dropout rate (ie, the fraction of participants not completing Week 16 assessment), 25 participants per group will still provide 78% power to detect a treatment difference of 30%.

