Treatment Arms and Duration:

Participants will be randomized to one of the following dose levels of BMS-986166 or branebrutinib or placebo in blinded fashion:

- BMS-986166 0.25 mg PO QD
- BMS-986166 0.50 mg PO QD
- BMS-986166 0.75 mg PO QD
- Branebrutinib 9 mg PO QD
- Placebo PO QD
- The first dose of double-blind study medication (BMS-986166 or branebrutinib or placebo) will be taken in the morning on Day 1 after fasting for at least 8 hours.
- Study medication should be taken at approximately the same time each day.
- Participants will take 3 capsules each day, one from each of 3 distinct bottles.

Study Treatment				
Treatment Group	Double-blind Kit	Bottle A	Bottle B	Bottle C
Placebo	Each kit contains Bottle A, Bottle B, Bottle C	Placebo capsule	Placebo capsule	Placebo capsule
`166 0.25 mg QD		`166 capsule, 0.25 mg	Placebo capsule	Placebo capsule
`166 0.5 mg QD		`166 capsule, 0.25 mg	`166 capsule, 0.25 mg	Placebo capsule
`166 0.75 mg QD		`166 capsule, 0.25 mg	`166 capsule, 0.25 mg	`166 capsule, 0.25 mg
BRA 9 mg QD		BRA capsule, 3 mg	BRA capsule, 3 mg	BRA capsule, 3 mg

Abbreviations: `166 = BMS-986166-04; BRA = branebrutinib; QD = once daily

Note: all capsules are identical in size (size 0).

Data Monitoring Committee: Yes

Statistical Considerations:

The sample size calculation is driven by the power to compare mean percentage change from baseline in EASI score at Week 16 between BMS-986166 or branebrutinib versus placebo. Thirty participants per group will provide 84% power to detect a treatment difference (versus placebo) of 30% at the type I error of $\alpha = 0.05$ (1-sided), assuming a common standard deviation of 43%. The assumed treatment difference of 30% is similar to the mean difference observed from historical data on approved drugs across different mechanism of actions. No adjustment will be made for multiplicity.

Assuming a 15% dropout rate (ie, the fraction of participants not completing Week 16 assessment), 25 participants per group will still provide 78% power to detect a treatment difference of 30%.

An interim analysis (IA) may be performed when approximately 50% of the participants have reached Week 16 or discontinued. Safety and efficacy analysis will be performed to accelerate internal decision making. The IA will be performed by individuals or vendor independent of the study team. The study team will remain blinded during IA.

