7.7.2 Rescue Therapy

Participants having intolerable symptoms within the first 4 weeks of treatment may use the below topical agents (according to their respective label instructions) as rescue therapy up until Week 4 according to the investigator's judgement.

- Fluocinolone acetonide 0.025%
- Hydrocortisone butyrate 0.1%
- Mometasone furoate 0.1%
- Triamcinolone acetonide 0.1%

Participants requiring and completing ≤ 7 days of topical rescue therapy within the first 4 weeks of IP treatment initiation, will remain eligible to be counted as responders for categorical efficacy endpoints; their numerical endpoints will also be counted as if they did not receive rescue therapy.

Participants either (1) requiring topical rescue therapy after 4 weeks of IP treatment, or for more than 7 days, or (2) requiring systemic corticosteroid/immunosuppression or phototherapy will discontinue from study treatment and be considered treatment failures for categorical endpoints.

Participants who discontinue study treatment are to remain in the study and complete all study visits and assessments unless they withdraw consent ([Section 8.2](#)).

Statistical handling of data from participants requiring rescue medication appears in [Section 10.3.1](#).

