10.3 Statistical Analyses

The statistical analysis plan will be developed and finalized before database lock and will include a more technical and detailed description of the statistical analyses described in this section. This

section is a summary of planned statistical analyses of the most important endpoints including primary and secondary endpoints.

A description of the participant population will be included in a statistical output report, including subgroups of age, gender and race.

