10.3.1 Efficacy Analyses

10.3.1.1 Primary Endpoint

The primary efficacy endpoint is mean percent change from baseline in EASI score at Week 16.

A mixed effect model will be fit with treatment, visit and treatment-by visit interaction as the fixed effects and measurements within each participant as the repeated measurements. Adjusted mean % change (LSMEAN) and unadjusted mean % change with corresponding 95% CI per treatment group will be provided. The difference in adjusted means and corresponding 95% CIs will be provided for the difference between active treatment groups and placebo group at different visits (week 16 for primary endpoints). P-value will be provided for difference at Week 16.

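### Does sizing the trial on a one-sided 5% test conflict with reporting the Week 16 EASI difference by 95% confidence intervals and a p-value of unstated sidedness?

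*Combined protocol and SAP*

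**What the plan says.** Section 10.1 bases the sample size on the mean percentage change from baseline in EASI at Week 16, each active group against placebo: "Thirty participants per group will provide 84% power to detect a treatment difference (versus placebo) of 30 % at the type I error" of 0.05. The sentence continues "1-sided), assuming a common standard deviation of 43" percent. After an assumed 15% dropout, "25 participants per group will still provide 78% power to detect a treatment difference of 30" percent. The Synopsis repeats the statement ("Thirty participants per group will provide 84% power to detect a treatment difference (versus placebo) of 30% at the type I error"), again one-sided at 0.05. Both places say that no multiplicity adjustment is made.

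The primary analysis in Section 10.3.1.1 is a repeated-measures mixed model. On the contrast with placebo it says: "The difference in adjusted means and corresponding 95% CIs will be provided for the difference between active treatment groups and placebo group", by visit, with Week 16 as the primary time point. It adds "P-value will be provided for difference at Week 16". It gives no sidedness, no threshold and no 90% interval.

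Section 10.3 describes itself as a summary and leaves the technical detail to a later document: "The statistical analysis plan will be developed and finalized before database lock". No separate plan is among the supplied documents.

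**The concern.** A one-sided test at 5% rejects exactly when the lower limit of the two-sided 90% interval lies above zero. A 95% interval excluding zero corresponds to a one-sided 2.5% test, which is harder to pass. A reader who treats the 95% interval in the report as the test would therefore be applying a stricter rule than the one that produced the 84% and 78%.

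A result could then pass the sizing test while its 95% interval covers zero, and Section 10.3.1.1 does not say how to describe such a result. The study is meant to inform whether one or both compounds advance, and there are four comparisons with placebo, so a borderline result is a realistic prospect.

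A second, smaller worry concerns rescue medication. Section 7.7.2 says "Statistical handling of data from participants requiring rescue medication appears in" Section 10.3.1, but the rule that sets values after rescue to missing is written under the secondary endpoints in Section 10.3.1.2. If it also covers the primary endpoint, the 15% allowance, defined by failure to complete the Week 16 assessment, would not count those values.

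**Working it through.** **Inputs** (Section 10.1): difference 30 points, common standard deviation 43 points, 30 or 25 per group, alpha 0.05 one-sided. Differences are written so that positive favours active treatment.

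**Step 1: reproduce the stated power.** The standard error of a difference is 43 × √(2/n), and the noncentrality is 30 divided by it.

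- n = 30: SE = 43 × √(2/30) = 11.10; noncentrality 30/11.10 = 2.70; 58 degrees of freedom.
- n = 25: SE = 43 × √(2/25) = 12.16; noncentrality 30/12.16 = 2.47; 48 degrees of freedom.

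Power from the noncentral t distribution:

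| Per group | Stated | One-sided 5% | 95% interval excludes zero |
|---|---|---|---|
| 30 | 84% | 84.7% | 75.7% |
| 25 | 78% | 78.4% | 67.6% |

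The one-sided column reproduces the protocol. The last column does not, so the stated figures were clearly computed for the one-sided test they name. Pooling the variance over five arms raises the last column to 76.6% and 68.7%. The normal approximation gives 77.1% and 69.4%.

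**Step 2: where the two readings part.** The smallest observed difference that passes is the critical t times the SE.

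- n = 30: 18.6 points (one-sided 5%) against 22.2 points (95% interval).
- n = 25: 20.4 points against 24.5 points.

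If the true difference is 30, the chance of falling between the two is 84.7 − 75.7 = 9.0 percentage points at 30 per group, and 78.4 − 67.6 = 10.8 at 25 per group.

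**Step 3: an example in that band.** Observed difference 20, n = 30, SD 43: t = 20/11.10 = 1.80.

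- One-sided p = 0.038; two-sided p = 0.077.
- 90% interval: 20 ± 18.6, or 1.4 to 38.6.
- 95% interval: 20 ± 22.2, or −2.2 to 42.2.

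The two p-values differ by a factor of two (0.038 × 2 is about 0.077), and the two intervals share the same centre and standard error. Whichever is printed, the other can be recovered from it once the p-value is labelled.

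**Step 4: is there a second success rule?** Section 10.1 and the Synopsis give one alpha, 0.05 one-sided. Section 10.3.1.1 gives none. It uses 95% intervals for each arm's adjusted and unadjusted mean as well as for the contrasts. Section 10.3.1.2 uses them for the secondary endpoints and plans no p-values there. This is a uniform format for estimates. The interim analysis in Section 10.3.4 uses the Bayesian probability that the difference exceeds some value, so it does not depend on the sidedness of the final p-value. Nothing ties a decision to the 95% interval.

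**The case for a change.** The strongest case for acting is that the choice is unstated, it can alter how a borderline result is described, and a sentence would settle it. Section 10.3 requires the statistical analysis plan only before database lock, whereas the interim analysis at about 50% of participants comes earlier and is reviewed by an unblinded sponsor team. It would be tidier to fix the reading of the p-value before that look.

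The omission is real, and so is the band of about 9 to 11 percentage points in Step 2. Labelling the p-value as one-sided, and the 95% intervals as descriptive, is sensible when the analysis plan is written. But that records what the protocol already implies. The unblinded team is kept out of study conduct and the study team stays blinded, so the timing creates no evident route to bias. Quoting 76% and 68% in Section 10.1 would give the power of a rule the plan does not adopt, and adding a 90% interval is largely a matter of presentation.

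The rescue point is also a question of wording. The cross-reference goes to Section 10.3.1, which holds both endpoint sections, and the rule speaks of continuous endpoints without restricting itself to secondary ones. The intended scope is reasonably clear. The documents give no rescue rate, so any loss of power would rest on assumed rates. A completers-only t-test would also ignore the visits before rescue that the planned mixed model uses.

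**Conclusion.** The concern does not hold as an inconsistency. The protocol names one test, a one-sided test at 5%, and its 84% and 78% are right for that test. The figures of about 76% and 68% describe a different rule and are useful only as background for a reader who looks at the 95% interval.

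What is missing is the sidedness of one p-value. Followed as written, the plan still yields valid estimates, intervals and a p-value that can be read against the only alpha declared. In an exploratory study with no multiplicity adjustment and a later analysis plan, analysts fill that gap sensibly without an amendment.

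The power figures assume a two-sample t-test and the protocol's own difference and standard deviation. The planned mixed model also uses earlier visits from participants who drop out, so the figures for 25 per group are approximate and may understate power. The conclusion would change if the analysis plan made a 95% interval excluding zero the condition for success; the documents supplied do not.

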10.2 Populations for Analyses

For purposes of analysis, the following populations are defined:

Population	Description
Enrolled	All participants who sign informed consent
Randomized	All participants who are randomized to a treatment
Treated	All participants who take at least 1 dose of study treatment
modified Intent-To-Treat (mITT)	All participants who are randomized and received at least one dose of study treatment
Safety	All randomized participants who take at least 1 dose of double-blind study treatment. Participants will be included in the treatment group they were randomized to, except in the following cases: 
 • If a participant received the same incorrect treatment throughout the study, then the participant will be analyzed based on the treatment received. • If a participant received study drug from more than one treatment group, and none of the administrations were consistent with the assigned randomized treatment group, then the participant will be analyzed based on the first non-placebo treatment received. • If a participant is randomized to placebo treatment and receives non-placebo treatment, then the participant will be analyzed based on the first non-placebo treatment received.
Pharmacokinetic	All participants who received any corresponding study drug and have any available concentration-time data
Biomarker	All participants that received any study treatment and have any available biomarker measurement

Safety analysis will be based on Safety population, participants will be analyzed as per actual treatment received. Efficacy analysis will be based on mITT population, participants will be analyzed as per randomized treatment.

10.3 Statistical Analyses

The statistical analysis plan will be developed and finalized before database lock and will include a more technical and detailed description of the statistical analyses described in this section. This

section is a summary of planned statistical analyses of the most important endpoints including primary and secondary endpoints.

A description of the participant population will be included in a statistical output report, including subgroups of age, gender and race.

10.3.1 Efficacy Analyses

10.3.1.1 Primary Endpoint

The primary efficacy endpoint is mean percent change from baseline in EASI score at Week 16.

A mixed effect model will be fit with treatment, visit and treatment-by visit interaction as the fixed effects and measurements within each participant as the repeated measurements. Adjusted mean % change (LSMEAN) and unadjusted mean % change with corresponding 95% CI per treatment group will be provided. The difference in adjusted means and corresponding 95% CIs will be provided for the difference between active treatment groups and placebo group at different visits (week 16 for primary endpoints). P-value will be provided for difference at Week 16.

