Abbreviations: AD = Atopic Dermatitis; BSA = Body Surface Area; CBC = Complete Blood Count; COVID-19 = coronavirus disease 2019; CXR = Chest X-ray; DLCO = Diffusion Capacity; DLQI = Dermatology Life Quality Index; EASI = Eczema Area and Severity Index; ECG = electrocardiogram; eCRF = Electronic Case Report Form; eGFR = estimated Glomerular Filtration Rate; FEV1 = Forced Expiratory Volume in 1 second; FVC = Forced Vital Capacity; FSH = Follicle Stimulating Hormone; HBcAb = Hepatitis B core antibody; HBsAb = Hepatitis B surface antibody; HBsAg = Hepatitis B surface antigen; HCV = Hepatitis C virus; HIV = Human Immunodeficiency virus; ICF = Informed Consent Form; INR = international normalized ratio; IRT = Interactive Response Technology; LH = Luteinizing hormone; NRS = Numerical Rating Scale; PA = Posteroanterior; POEM = Patient Oriented Eczema Measure; PPE = Personal Protective Equipment; PT = prothrombin time; RT-PCR = Reverse transcriptase polymerase chain reaction; SAE = Serious Adverse Event; SARS-CoV-2 = severe acute respiratory syndrome coronavirus 2; TB = Tuberculosis; UA = urinalysis; vIGA-AD = validated Investigator Global Assessment scale for Atopic Dermatitis; WOCBP = Women of Childbearing Potential.

Table 2-2: On-treatment Procedural Outline (IM018005)

Procedure	Day 1 ^a (Rand)	Day 8 W1 (± 1 days)	Day 15 W2 (± 3 days)	Day 29 W4 (± 3 days)	Day 57 W8 (± 3 days)	Day 85 ^a W12 (± 3 days)	Day 113 (EOT) W16 (± 3 days)	Notes
Administrative and Historical Assessments								
Inclusion/Exclusion Criteria	X							Review of inclusion/exclusion criteria that are specified on or defined relative to the randomization day
Randomization via IRT	X							
Disease/Efficacy Assessment								
EASI	X	X	X	X	X	X	X	EASI at baseline must be ≥ 16 (prior to randomization).
vIGA-AD	X	X	X	X	X	X	X	
BSA Assessment	X	X	X	X	X	X	X	
Pruritus and Sleep Quality NRS	X	X	X	X	X	X	X	Will be collected daily in an electronic diary – represents preceding 24 hours. Data will be collected at each specified visit.
DLQI	X	X	X	X	X	X	X	Data will be collected at each specified visit.
POEM	X	X	X	X	X	X	X	
PGI-S	X	X			X		X	
PGI-C		X			X		X	
Pulmonary Function Test				X			X	FEV1, FVC & DLCO may be collected within a window of ± 5 days of visit.
Visual Acuity Testing and Optical Coherence Tomography					X		X	May be collected within a window of ± 7 days of visit.
Safety Activities								
Body Weight	X						X	

Table 2-2: On-treatment Procedural Outline (IM018005)

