10.3.1.2 Secondary Endpoint

The secondary efficacy endpoints are:

- Proportion of participants exhibiting a vIGA-AD score of 0 (cleared) or 1 (almost cleared) AND a ≥ 2 point reduction from Baseline at Week 16;
- Proportions of participants exhibiting a $\geq 50\%$ (EASI-50) reduction from baseline in EASI score at Week 16
- Proportion of participants exhibiting a ≥ 4 point improvement from baseline in Pruritus NRS at Week 16.
- Mean percentage change from baseline in Pruritus NRS at Week 16
- Mean change from baseline in percentage of affected BSA at Week 16

For categorical (proportion) endpoints, the estimate and its corresponding 95% CI of each treatment group will be estimated using Clopper-Pearson method. The difference of the proportion between active treatments and the placebo will be estimated and their corresponding 95% CI will be calculated.

All participants discontinuing prematurely prior to Week 16, regardless of reason, will be counted as non-responders at subsequent visits.

For continuous (percent change from baseline and change from baseline) endpoints, the similar mixed effect model (as used in [Section 10.3.1.1](#)) will be fit with treatment, visit, and treatment-by visit interaction as the fixed effects and measurements within each participant as the repeated measurements. The baseline value will be added into the model as a covariate if necessary, for change from baseline endpoints. Adjusted mean % change (LSMEAN) and unadjusted mean % change with corresponding 95% CI per treatment group will be provided. The difference in adjusted means and corresponding 95% CIs will be provided for the difference between active treatment groups and placebo group at specific visits (eg, week 16 for secondary endpoints).

For participants requiring topical rescue therapy after the first 4 weeks of treatment or for more than 7 days, efficacy assessment after administration of rescue therapy will be considered as missing for continuous endpoints and considered as non-responder for categorical endpoints.

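### The primary mixed model leaves out baseline EASI, and baseline is only conditional for the secondary endpoints; prespecifying it costs almost nothing and may gain a little precision

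*Combined protocol and SAP*

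**What the plan says.** Section 10.3.1.1 defines the endpoint and the model: "The primary efficacy endpoint is mean percent change from baseline in EASI score at Week 16", and "A mixed effect model will be fit with treatment, visit and treatment-by visit interaction as the fixed effects". No baseline term follows.

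Section 10.3.1.2 uses a similar model for the continuous secondary endpoints. It first names two classes: "For continuous (percent change from baseline and change from baseline) endpoints". It then says: "The baseline value will be added into the model as a covariate if necessary, for change from baseline endpoints". It does not say what would make the covariate necessary.

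Baseline EASI exists for everyone, because Table 2-2 makes it an entry condition on Day 1: "EASI at baseline must be ≥ 16 (prior to randomization").

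Section 10.3 leaves technical detail for later: "The statistical analysis plan will be developed and finalized before database lock". The supplied documents contain no further SAP text on this point.

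**The concern.** If baseline severity predicts response, a model with baseline gives a narrower interval for each active-versus-placebo difference, from data the trial already collects. With 30 per arm, and about 25 after dropout, chance imbalance in baseline severity is also more likely than in a large trial, and the planned model does not adjust for it.

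Missing data are a second reason. Section 10.1 allows for 15% of participants without a Week 16 assessment. For participants who use topical rescue after Week 4 or for more than 7 days, Section 10.3.1.2 adds that "efficacy assessment after administration of rescue therapy will be considered as missing for continuous endpoints". With baseline in the model, missingness that depends on baseline severity is covered directly by the missing-at-random assumption. Without it, that holds only as far as earlier post-baseline scores carry the same information.

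Third, the secondary models are left open. Read literally, baseline is optional for change in affected BSA and absent for percent change in pruritus NRS. On a looser reading it is optional for both. Either way the rule can be settled after data have accrued.

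**Working it through.** **Inputs.** From Section 10.1: difference 30 points, SD 43, one-sided alpha 0.05, 30 per group, and 25 per group after 15% dropout. Allocation is equal across five arms (Section 5.1.2). The correlation r between baseline EASI and Week 16 percent change is not in the documents; r from 0 to 0.5 is an assumption.

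**Step 1: reproduce the stated power.** SE = 43 × √(2/n), which is 11.10 at n = 30 and 12.16 at n = 25. Noncentral t with noncentrality 30/SE and df = 2n − 2 (58 and 48) gives 84.7% and 78.4%, against the stated 84% and 78%. No covariate is needed to reach those figures.

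**Step 2: five-arm model, unadjusted.** The residual df are 150 − 5 = 145 and 125 − 5 = 120. Power is 85.2% and 79.0%.

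**Step 3: add baseline.** The residual SD becomes 43 × √(1 − r²) and one df is lost. Estimating the slope multiplies the variance of the difference by 1 + 1/(ν − 2), where ν is the unadjusted residual df:
- n = 30: 1 + 1/143 = 1.0070
- n = 25: 1 + 1/118 = 1.0085

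The net variance ratio is (1 − r²) times that factor. For example, at r = 0.3 and n = 30 it is 0.91 × 1.0070 = 0.916, so the SE is 11.10 × √0.916, or about 10.63.

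| r (assumed) | Variance ratio, n = 30 | SE, n = 30 | Power, n = 30 | Variance ratio, n = 25 | SE, n = 25 | Power, n = 25 |
|---|---|---|---|---|---|---|
| no baseline | 1 | 11.10 | 85.2% | 1 | 12.16 | 79.0% |
| 0 | 1.007 | 11.14 | 85.0% | 1.008 | 12.21 | 78.7% |
| 0.1 | 0.997 | 11.09 | 85.3% | 0.998 | 12.15 | 79.1% |
| 0.2 | 0.967 | 10.92 | 86.2% | 0.968 | 11.97 | 80.2% |
| 0.3 | 0.916 | 10.63 | 87.8% | 0.918 | 11.65 | 82.0% |
| 0.5 | 0.755 | 9.65 | 92.6% | 0.756 | 10.58 | 88.0% |

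**Step 4: break-even.** Setting (1 − r²) × factor = 1 gives r = √(1 − 1/factor) = 0.083 at n = 30 and 0.092 at n = 25. Below that, adjustment costs slightly more than it returns.

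**Step 5: simulation of power.** Five arms, complete Week 16 data, 40,000 trials per cell. At n = 30, adding baseline moved power from 84.9% to 84.7% at r = 0 and from 85.3% to 92.6% at r = 0.5. At n = 25 it moved from 79.1% to 78.8% at r = 0 and from 79.0% to 82.0% at r = 0.3. These agree with the table.

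**Step 6: validity.** In a two-arm simulation with complete data at r = 0, 0.3 and 0.5, one-sided type I error without baseline was 0.050 to 0.051, with no material bias. A second null simulation set about 15% of values to missing. When missingness depended on baseline in the placebo arm only, the unadjusted estimate was biased by 1.8 points at r = 0.3 and 3.2 points at r = 0.5; the adjusted estimate showed no material bias. When the dependence was the same in both arms, neither estimate had material bias.

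No figure is given for BSA or pruritus NRS, because the documents state no SD for either.

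**The case against.** The strongest reply is that nothing is wrong with the primary analysis. It holds its error rate, the sample size does not rely on a covariate, and percent change already divides by baseline. Leaving baseline out of percent-change models while allowing it for absolute change is a coherent choice. All of that stands, and it is why the point is graded as minor.

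The gain also rests on an assumed r. The gains of 7 to 9 points need r = 0.5, which nothing in the documents supports, and the entry floor on EASI restricts the baseline range, which tends to lower a correlation. This stands too. It limits the likely benefit but does not create a real cost.

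The missing-data argument is weaker than the simulated bias suggests. EASI is scored at Weeks 1, 2, 4, 8 and 12 as well as Week 16, and the repeated-measures model uses those scores. The simulation had no intermediate visits and produced bias only when missingness depended on baseline differently by arm. The bias figures are illustrative and are not a forecast for this trial.

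Finally, the SAP could still settle the covariates before lock, with the study team blinded at the interim analysis (Section 10.3.4). That shows where the change can be made. However, Section 10.3 presents the SAP as a fuller account of the analyses it already describes, and a SAP faithful to Section 10.3.1.1 would still omit baseline EASI.

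**Conclusion.** The concern holds, as a minor point. The primary model omits an available prognostic candidate, and the rule for the secondary models has no criterion. The planned primary comparison remains valid under randomization.

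Under the plan's own difference and SD, adding baseline costs 0.2 to 0.3 points of power at r = 0 (a variance cost of 0.7% to 0.8%). It gains about 1 point at r = 0.2, about 3 points at r = 0.3, and 7 to 9 points at r = 0.5. These figures assume complete Week 16 data for the stated number per arm and a linear baseline effect. Because the endpoint is already scaled by baseline, the lower end of the range is quite possible. The gain is plausibly larger for absolute change in BSA, but it cannot be sized from the documents.

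**What to change.** - **Section 10.3.1.1:** list the fixed effects as treatment, visit, treatment-by-visit, baseline EASI and baseline EASI-by-visit.
- **Section 10.3.1.2:** remove the conditional clause. Require each continuous endpoint's own baseline value and its interaction with visit, for both percent change in pruritus NRS and change in percentage of affected BSA.
- **Supportive display:** keep the unadjusted means already planned.
- **SAP:** carry the same wording over.

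The cost is wording in the protocol and SAP. No data, visits or participants are added. The statistical downside is a variance cost under 1% in the five-arm model if r is near zero.
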